Post-Treatment Assessment	Pain interference, pain catastrophizing, cognitive processes, activity level, average pain intensity, mood, physical function, sleep, depression, anxiety, PTSD, medication and cannabis use, pain self-efficacy, health care use, disability due to chronic pain, engagement in pleasurable events, engagement in activities, global quality of life, employment status, weight, mindfulness, pain resilience, pain beliefs, perceived cognitive abilities, time spent practicing coping skills, treatment satisfaction, treatment modality, overall participant improvement since beginning treatment, open-ended items about experiences in group and feedback about program, pain medication beliefs, and COVID-19 effects Optional Items: Responses to pain, goals, and future expectations	Once following end of treatment; allowable window of up to 2 months after end of treatment
3-Month Assessment	Pain interference, pain catastrophizing, cognitive processes, activity level, average pain intensity, mood, physical function, sleep, depression, anxiety, PTSD, medication and cannabis use, pain self-efficacy, health care use, disability due to chronic pain, engagement in pleasurable events, engagement in activities, global quality of life, employment status, weight, mindfulness, pain resilience, pain beliefs, perceived cognitive abilities, time spent practicing coping skills, treatment satisfaction, overall participant improvement since beginning treatment, pain medication beliefs, and COVID-19 effects Optional Items: Responses to pain, goals, and future expectations	Once three months following end of treatment; allowable window of 2-5 months after end of treatment

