6-Month Assessment	
Pain interference, pain catastrophizing, cognitive processes, activity level, average pain intensity, mood, physical function, sleep, depression, anxiety, PTSD, medication and cannabis use, pain self-efficacy, health care use, disability due to chronic pain, engagement in pleasurable events, engagement in activities, global quality of life, employment status, weight, mindfulness, pain resilience, pain beliefs, perceived cognitive abilities, time spent practicing coping skills, treatment satisfaction, overall participant improvement since beginning treatment, pain medication beliefs, and COVID-19 effects
 
Optional Items: Responses to pain, goals, and future expectations
	
Once six months following end of treatment; allowable window of 5-8 months after end of treatment

---------------------------	---	--

* Will only be administered if participant is still eligible after Pain Interference Re-Assessment

** Only participants who have completed all required baseline study procedures will be randomized. Required procedures include: Baseline Data, Demographics, Pre-Treatment Assessment, Technology Training, Pain Interference Re-Assessment and Randomization Stratification, and completion of a minimum number of EMA surveys.

D2. Study Timeline

We designed a five-year study plan and timeline for achieving short-term study objectives. There will be approximately 42 months available to enroll 300 participants, with 240 participants projected to complete all study elements.

Months 01-12 in Year 01 will be spent hiring staff, finalizing treatment manuals for delivery via Zoom (including adapting workbooks into PowerPoint slides), creating databases, developing and testing the EMA system, and developing internal operating procedures surrounding the study. Participant enrollment will require approximately 3.5 years (42 months; Month 01, Year 02 through Month 06, Year 05). Data collection and cleaning will be ongoing through Month 12, Year 05. Data analysis and dissemination will occur following data collection and cleaning. Drs. [name] and [name] will closely monitor study flow and will hold regular conference calls to coordinate study procedures. Both PIs will be directly involved with the details of the study at every level. Intra-site team meetings with staff and Co-Is will be conducted to ensure any issues will be addressed as they arise.

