Staff will send the participant a reminder through his/her preferred method of communication prior to the 3- and 6-month assessment periods. All scheduled telephone assessments will be completed at a time deemed mutually agreeable by both the participant and research staff. For assessments completed online, the participant will be allowed to independently complete the assessment on their own time, with limits set by researchers on how long they may spend completing the assessment (e.g., once opened, the assessment must be completed within 24 hours, 48 hours, etc.). If a participant starts an assessment within window for an assessment period but continues to provide data for that assessment after the window closes, researchers will keep the out-of-window data. This scenario could occur if the participant, for example, begins an assessment over the phone or online, has to stop, and does not complete the remainder of the assessment until after the window has closed. Although research staff have internal protocols on reminding participants a reasonable number of times to complete unfinished and partial assessments, it is ultimately on the participant to agree to finish what they started. In some cases, participants may have circumstances that prevent them from timely finishing what they started in window, despite the best efforts of research staff. Collecting and retaining the out-of-window data will NOT be considered a protocol deviation.

As mentioned above, during the consent process research staff will provide participants with a response key to help answer questions asked during the telephone assessment periods. Participants may request research staff send another response key to them if they lose the key during study participation. Research staff will send the response key along with a cover letter if the participant requests it via USPS mail or through email if the participant prefers email.

Participants will be compensated \$25 for the completion of each assessment period via a check. The check will be sent via USPS mail and accompanied by a payment cover letter.

D6h. Optional Assessments

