We will replicate the analyses used to test Aims 1 and 2 to (1) evaluate the role of secondary mechanism variables (other mindfulness facets, pain acceptance, pain beliefs, therapeutic alliance, self-reported activity level, and client engagement) on primary outcomes and (2) the effects of the mechanism variables on secondary outcome measures (pain intensity, mood, physical functioning, sleep quality, morphine equivalent, health care use). We will also examine longer (macro) follow-up mechanism effects using the 3- and 6-month follow-up data. Specifically, we will perform a further three-wave SEM model (as described above) to determine if post-treatment to 3-month follow-up changes in the primary and secondary mechanism variables predict subsequent 3-month to 6-month changes in the primary and secondary outcomes. We will also explore the potential role of participants' emotional responses to COVID-19 in relation to outcome and tests of mechanism.

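### The exploratory 3- and 6-month mechanism model names no elapsed-time term, although the visit windows let its two intervals run from 0 to 5 and 0 to 6 months; with post-treatment drift this mainly hides or reverses a mechanism

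*Combined protocol and SAP*

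**What the plan says.** Table 1 (Study Design) sets the timing of the three extended assessments:

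- Post-treatment: "Once following end of treatment; allowable window of up to 2 months after end of treatment".
- 3-month: "Once three months following end of treatment; allowable window of 2-5 months after end of treatment".
- 6-month: "Once six months following end of treatment; allowable window of 5-8 months after end of treatment".

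Section D6g adds that an assessment begun inside its window may be finished after the window closes, and that the late answers are kept: "Collecting and retaining the out-of-window data will NOT be considered a protocol deviation". This covers only assessments started in window.

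Section D6s, under Additional Exploratory Analyses, then plans a further three-wave model, built as described earlier in that section. It asks whether "post-treatment to 3-month follow-up changes in the primary and secondary mechanism variables predict subsequent 3-month to 6-month changes" in the primary and secondary outcomes. The method described earlier in D6s was written for the daily diary and ActiGraph epochs and rescales time to run from 0 to 1 within each epoch. D6s also has a general statement that relevant covariates will be tested and controlled for where indicated. It does not name assessment date or elapsed time, and neither document section sets a minimum gap between assessments or a sensitivity analysis for visit timing.

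**The concern.** Rescaling each epoch to 0-1 suits the daily-data epochs of D6s, which are each about two weeks long. It does not carry over to visits with windows two or three months wide. With one assessment at each end of an interval, a slope on a 0-1 scale is the raw difference, so a change over a few days and a change over five months count alike.

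The unequal spacing is more than noise. The 3-month date closes the first interval and opens the second, so the interval lengths are negatively linked. If scores move on average after treatment, people with a long first interval show more mechanism change and, having a shorter second interval, less outcome change. This creates an association unrelated to any mechanism. The protocol itself expects movement: section B.1.4 cites declines in treatment gains within about a month of treatment. At stake is the one planned model that addresses longer-term maintenance of gains.

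**Working it through.** **Inputs from the documents.** Windows of 0-2, 2-5 and 5-8 months after end of treatment (Table 1); N = 240 (D6u). The plan gives no power or effect figure for this model, so there is none to reproduce.

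**Range of the intervals.**
- Post-treatment to 3-month: minimum 2 - 2 = 0, maximum 5 - 0 = 5 months.
- 3-month to 6-month: minimum 5 - 5 = 0, maximum 8 - 2 = 6 months.

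**Spread and linkage (timing assumed).** Let t1, t2, t3 be independent visit times, d1 = t2 - t1 and d2 = t3 - t2. Then Cov(d1, d2) = -Var(t2).
- *Visits uniform in their windows.* Var(t1) = 4/12 and Var(t2) = Var(t3) = 9/12. Var(d1) = 1.083 (SD 1.04, mean 2.5); Var(d2) = 1.5 (SD 1.22, mean 3.0). Correlation = -0.75/√(1.083 × 1.5) = -.59.
- *Visits triangular, peaked at the nominal dates (0, 3 and 6 months).* Var(t1) = 4/18 and Var(t2) = Var(t3) = 7/18. SDs are .78 and .88, means 2.67 and 3.0, correlation -.56.

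**Bias in the raw-change association.** Suppose each person's mechanism and outcome move linearly, with independent slopes (mean μ, SD σ_s) and assessment error SD σ_e. Then:
- Cov(change 1, change 2) = -μ_M μ_Y Var(t2).
- Var(change k) = σ_s²(E[d_k]² + Var(d_k)) + μ² Var(d_k) + 2σ_e².

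Worked example with μ = .2 for both, σ_s = .1, σ_e = .3 and uniform visits:
- Covariance = -.04 × .75 = -.030.
- Var(change 1) = .01 × 7.333 + .04 × 1.083 + .18 = .297.
- Var(change 2) = .01 × 10.5 + .04 × 1.5 + .18 = .345.
- r = -.030/√(.297 × .345) = -.094. With N = 240, z ≈ .094 × √238 = 1.45, so about 30% of trials reject at two-sided .05, almost all with a negative sign.

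**Direction.** The artefact has the sign of -μ_M μ_Y. Catastrophizing and interference are expected to move together, so joint relapse or joint gain gives a negative artefact against a positive hypothesis. Non-judgment and activity are expected to move opposite to interference, so coherent drift gives a positive artefact against a negative hypothesis. Only incoherent drift (for example, mechanism improving while outcome worsens) pushes towards the hypothesis.

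**Simulation over a grid.** N = 240, unrelated mechanism and outcome, σ_s .1-.2, σ_e .3-.5, rejection at two-sided .05:

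| Drift per month | Uniform visits | Triangular visits |
|---|---|---|
| .1 | near nominal | near nominal |
| .2 | about 8-29% | within the overall range |
| .3 | about 19-80% | up to about 37% |

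Overall, triangular visits give about 5-37%. By the formula, the spurious correlation under uniform visits runs from about -.01 to -.18. Entering d1 and d2 as covariates returns rejection to about 3-6% in every setting. In one run with a true effect of assumed size and drift of .2, power rose from 52% without the intervals to 87% with them; only the direction of that comparison should be relied on.

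**Why not change per month.** Dividing by the interval gives an error variance of 2σ_e² E[1/d²]. Under uniform visits the density of d1 near zero is about d/6, so ∫ (1/d²)(d/6) dd diverges. A few short gaps would dominate the analysis.

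**The case against.** Several points on the other side stand.

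- The analysis is exploratory, and D6s says such results will be presented as needing confirmation. D6u says secondary analyses will be discussed by effect size, so a rejection rate is an imperfect measure of harm. The bias is in the coefficient itself, however, so reading effect sizes does not avoid it.
- Visits are aimed at nominal dates with reminders, so uniform timing is unfavourable. Gaps near 0, 5 or 6 months are permitted; nothing shows they are common. With clustered visits the distortion is smaller, and at low drift it is negligible.
- No sentence says that all intervals are equal. That is inferred from the 0-1 coding and from silence on elapsed time. The model diagram is not available here, so whether prior levels are controlled is unknown, and the calculation uses a plain raw-change association. The general covariate sentence could admit visit timing but does not prespecify it.

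A reader might infer more than the documents support:

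- *That the plan risks manufacturing support for the hypothesised mechanisms.* With coherent drift the sign is the wrong one for that; loss or reversal of a true path is the main risk.
- *That any late visit is kept freely.* D6g keeps late data only when the assessment began in window, and F4a still counts visits completed outside the windows as deviations.
- *That moving from telephone to online at follow-up is a demonstrated bias.* D6g states that the items are the same, and nothing in the documents quantifies a mode effect.

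**Conclusion.** The concern holds as a minor point about an exploratory model. The interval ranges of 0-5 and 0-6 months follow directly from Table 1, as does their linkage through the shared 3-month date, given visit times that vary independently. Followed as written, the model would give a distorted path whenever mechanism and outcome both drift after treatment. Under coherent drift the distortion opposes the hypothesis.

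Its size cannot be fixed from the documents. Timing, drift, slope variance and error variance are all assumptions, in unspecified scale units; a drift of .3 a month against an error SD of .3-.5 is a strong one. The results run from no visible effect to a serious one, and the grid should be read as that range and not as a forecast. Aims 1 and 2 rest on daily epochs over days 1-70 and are untouched.

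**What to change.** Add a few sentences to D6s for the 3-/6-month model:

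1. Enter the two actual elapsed intervals as covariates, or enter actual months since end of treatment as individually varying times of observation.
2. Add a sensitivity analysis that excludes closely spaced pairs of assessments, with the cutoff stated in advance.
3. Do not use change per month.
4. Optionally, add a telephone/online indicator at the 3- and 6-month waves. At post-treatment the assessment is by telephone, so an indicator there would be constant.

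The cost is SAP wording and a slightly more complex model. Assessment dates must already be held, since F4a identifies visits outside their windows. Mode should be recoverable from whether staff or the participant completed the REDCap form (D6r), although no section says it is stored as a variable. Visit windows and sample size need not change.

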Because it is likely that we will encounter at least some missing data despite procedural efforts by research staff to minimize its occurrence, we have attempted to further address missing data in a number of ways via our data analysis approach. First, we will examine potential patterns of missing data that represent confounds contributing to biased slopes. So, for each participant, analyses to identify potential patterns in missing data will be conducted to determine if they are “ignorable” (see Schafer & Grahem, 2002)¹⁰⁷. If >5% of the participants do not provide adequate data, the sample will be divided into two groups (missing data, no missing data) and fully observed variables will be examined to determine if they significantly predict missingness on the affected outcome. This test will be done on a variable-by-variable basis. If this analysis is non-significant, the missingness will be considered “observed at random” and the procedures described below for calculation of slope coefficients in the instance of missing data will be used, without necessitating the use of multiple imputation procedures. However, if no data is available to calculate slope via the below methods, in Mplus, the missing data (slopes and estimated end values from slopes) are treated automatically (by default) by estimating the full model from available data using full information maximum likelihood (FIML). The Mplus robust maximum likelihood (MLR) estimator using FIML permits missing completely at random (MCAR) and missing at random (MAR), and MLR uses SEs that are corrected for non-normality and also uses a corrected chi-square fit statistic. If data missingness is not ignorable, Heckman’s selectivity models of pattern-mixture models with multiple imputation will be used to model the “missingness” for each participant before calculation of slopes from the daily EMA and ActiGraph data.

There are several ways to treat data that are deemed to be missing at random (from the daily EMA and ActiGraph data) using the slope method. For example, consider the six cases below (from real data). The dependent variable was measured at five equally spaced intervals within the epoch. Within the current study, there are additionally two observations per day, and we propose to calculate the slopes from morning and evening observations, and to average those slopes.

Cases	0	0.25	0.5	0.75	1	Slope	Difference
1	12	14	15	15	10	-1.2	-2
2	12	10	11	10	7	-4	-5
3	23	19	13	13	12	-11.2	-11

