4	15	16	12	13	8	-6.8	-7
5	29	21				-32	
6	21	22	15	20	12	-8	-9

In the above example, for Case 5, the slope is estimated to be -32, because it is based on the first two Time points, where there is a substantial decline. The decline is magnified by extrapolating the line over the full time period, and the score is probably an outlier. Hence, there are weaknesses to the slope method. However, one approach is to carry the last observation forward and first observation backward when there are missing data at the beginning or end of an epoch. The difference for Case 5 would then be -8 and the slope would be -6.15. Given there are four epochs in the current study, this method becomes somewhat complicated. However, we propose to carry forward or carry backward the closest score in the full sequence of scores from the beginning of pre-test to the end of post-test.

D6u. Power Analyses

We will conduct **six primary** statistical tests to test the primary aim for three mechanism variables, in order to better understand the effects of the treatments on pain interference. Data from prior research – including means and standard deviations – was used to support the anticipated medium to strong effects of the mechanism paths that we propose to test, and which form the basis of our assumptions for the power analyses.

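### The D6t test of whether observed variables predict missingness cannot separate MAR from MNAR, yet it decides how missing data in the primary slopes are handled

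*Combined protocol and SAP*

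**What the plan says.** All of this is in the combined protocol and SAP, section D6t (Missing Data), unless noted.

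- **Trigger.** "If >5% of the participants do not provide adequate data", the sample is split into those with and without missing data.
- **Test.** Then "fully observed variables will be examined to determine if they significantly predict missingness on the affected outcome". No alpha and no list of variables is given, and no other operational test of ignorability appears. On how the testing is organised, the plan adds only this: "This test will be done on a variable-by-variable basis".
- **Non-significant result.** "If this analysis is non-significant, the missingness will be considered" observed at random. The slope procedures then apply "without necessitating the use of multiple imputation procedures".
- **Slope procedures.** Where scores are missing at the start or end of an epoch, "we propose to carry forward or carry backward the closest score in the full sequence of scores".
- **FIML.** It enters only "if no data is available to calculate slope via the below methods". The same paragraph says that the estimator allows for both MCAR and MAR.
- **Not ignorable.** Heckman's "selectivity models of pattern-mixture models with multiple imputation will be used to model the" missingness for each participant before slopes are computed.
- **Significant result.** No sentence says what follows.

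D5 plans 300 enrolled and 240 complete, assuming 20% dropout. D6s says two ratings per epoch are enough to compute a slope.

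**The concern.** Missingness is MAR when it can depend on observed data but, given those data, not on the unobserved values. Finding that an observed variable predicts missingness is therefore no evidence against MAR. It shows which variable the analysis should condition on. Missingness is MNAR when it depends on unobserved values even after that conditioning, and a comparison of observed variables cannot show or exclude this.

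The D6t rule uses such a comparison to choose the missing-data method. A non-significant result certifies data as at random when they may be MNAR. A significant result takes data that may be plainly MAR out of the only at-random route described. In neither case does a rule carry the predictors of missingness into the model.

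The affected quantities are the early- and late-treatment slopes, and so the a and b paths on which the Shared and Specific Mechanisms conclusions rest. If the test is run separately for each variable with missing data, two variables in one SEM could also be handled under different missingness assumptions.

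**Working it through.** The plan gives no figure for this rule, so there is none to reproduce. The checks below show how the rule behaves. Alpha (.05, two-sided), effect sizes and numbers of tests are assumptions, because the plan states none of them.

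**1. Routing under the text.**

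| True mechanism | Likely test result | Route in D6t | Problem |
|---|---|---|---|
| MCAR | mostly non-significant | slopes and carrying; FIML if no slope | false triggers possible |
| MAR, observed predictor | significant if power allows | not written; by structure Heckman or pattern-mixture | FIML conditioning on the predictor would do |
| MNAR, unrelated to observed variables | mostly non-significant | slopes and carrying; FIML if no slope | certified as at random |

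**2. Power to find a real predictor.** Compare missing (n1) with observed (n2) on one variable with standardised difference d = 0.4. The noncentrality is d·√(n1·n2/(n1+n2)), used in a two-sample t test. The smallest counts above 5% are 13 of 240 (5% is 12) and 16 of 300 (5% is 15). At the planned 20% dropout, 300 × 0.20 = 60.

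- 13 missing, 227 observed: 0.4 × √(13×227/240) = 1.40; power about 29%.
- 16 missing, 284 observed: 0.4 × √(16×284/300) = 1.56; power about 34%.
- 60 missing, 240 observed: 0.4 × √(60×240/300) = 2.77; power about 79%.

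For d = 0.3 and 0.5 the powers are 18% and 42% (13 of 240), 21% and 49% (16 of 300), and about 54% and 93% (60 of 300). At or below 5% missing, no test is made.

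**3. False triggers under MCAR.** With k independent unadjusted tests the chance of at least one significant result is 1 − 0.95^k.

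- k = 1 (one joint test): 5%.
- k = 5: 23%.
- k = 10: 40%.

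If the multiplicity procedure in D6s covers these tests, the chance is about 5% whatever k is (simulated at 5.0% for 5 tests and 4.9% for 10).

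**4. Simulation of the rule.** N = 300, 1,000 runs, one observed variable X, outcome Y = 0.5X + e with unit variance, logistic missingness.

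- *MAR (depends on X), 20% missing.* The test is significant in 51%, 91% and 100% of runs for log-odds of 0.3, 0.5 and 1.0 per SD of X.
- *MNAR (depends only on e), 6% or 20% missing.* The test is significant in 4–5% of runs, so about 95% are labelled at random. The bias in the mean of Y is about −0.08 SD (log-odds 0.5) and −0.15 SD (log-odds 1.0) at 20% missing, and −0.02 and −0.05 SD at 6%.
- *Estimators under MAR, log-odds 1.0, 20% missing.* Available-case bias is −0.09 SD. The regression equivalent of FIML, conditioning on X, has bias 0.00 and an empirical SE of 0.06. Heckman two-step without an exclusion restriction has an empirical SE of 0.39, so 0.39/0.063 ≈ 6 times larger.

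The simulation concerns the mean of one outcome. It does not reproduce the SEM or the carrying of scores, and its sizes are not forecasts for this trial.

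**The case against.** The strongest objection is that D6t never says a significant result means non-ignorable. It assigns only the non-significant result, and the sentence on non-ignorable missingness stands apart, after the statement that FIML covers MAR. A reader might infer that the plan expressly sends all MAR data to Heckman models. The text does not support that: the routing is inferred because no other ignorability test and no other branch is given. On the kindest reading the significant branch is undefined and the method would be chosen after seeing the data. This narrows the point but does not remove it, because the non-significant branch is written out and is invalid on any reading.

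Other objections stand in part:

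- **False triggers.** A reader might quote 40% as the rate. That needs ten independent, unadjusted tests. The instruction to work variable by variable may instead mean one joint test per affected outcome, and D6s applies its multiplicity procedure to all analyses, although it goes on to describe it for the primary ones. Only the range of 5% to 40% is supportable.
- **Base for power.** A reader might take 20% of 240 as missing (48 against 192, power 69%). But 240 is already the number left after dropout, so 60 of 300 is the consistent pairing.
- **Amount missing.** Dropout of 20% need not mean that 20% lack adequate data. Two ratings per epoch suffice for a slope, and D6m keeps collecting data after treatment withdrawal.
- **Bias in FIML.** A reader might infer that FIML here is biased because non-significant predictors are dropped. No rule enters or drops predictors by significance. FIML conditions on every variable in the model, and bias requires an omitted predictor that is still related to the outcome given those variables. FIML is also the fallback, not the first step.
- **Covariates.** D6n adds covariates from comparing dropout between arms, and D6s mentions relevant covariates in general. Neither is tied to predictors of missingness, so the mitigation is partial.

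**Conclusion.** Wrong as written. The non-significant branch certifies data as at random on evidence that cannot bear on MNAR. The significant branch is unwritten and, by structure, leads to non-ignorable models for data that MAR methods may handle. That second part is an inference from structure and should be stated as one.

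On size, at alpha .05 and d = 0.4 a real predictor is found about 29% of the time with 13 of 240 missing, 34% with 16 of 300 and 79% with 60 of 300. The false-trigger chance under MCAR is 5% to 40%, depending on choices that the plan leaves open. When missingness is MNAR and unrelated to the observed variables, about 95% of datasets pass as at random. The effect on the trial's estimates depends on how much is missing and why, which the documents cannot tell us. The point should be corrected before analysis, but it does not show that the primary results will be biased.

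**What to change.** 1. Delete the significance test as the trigger for choosing a method. Missingness can still be described by arm and by baseline variables.
2. In all three SEMs use FIML or multiple imputation under MAR with auxiliary variables named in advance and already collected: baseline pain interference, the baseline mechanism variables, sex, LBP type, week-1 EMA completion and session attendance. Enter them as auxiliaries for the missing data. Attendance in particular arises after randomisation and should not become an adjustment covariate.
3. Apply the same approach to partial EMA and ActiGraph data, in place of carrying the nearest score forward or backward. Otherwise carried scores turn partial records into apparently observed slopes, and step 2 would reach few participants.
4. Run the pattern-mixture analysis as a pre-planned MNAR sensitivity analysis for each SEM, whatever any test shows, with the size of the shifts set in advance.

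The cost is revised SAP wording, imputation or modelling at the level of individual ratings, and one further sensitivity run per SEM. No new data are needed.
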